If the PI, MM, and GSO or designee decide not to proceed with enrollment into a subsequent cohort, then a Safety Review Meeting or DLRM will be held after the last dosed cohort. Refer to Section 10.4.2 for additional information on the Safety Review Meetings and DLRMs. The Safety Review Meeting or DLRM voting members will decide whether or not to proceed with enrollment in Part B Randomization (AMG 334 or Placebo) Phase and if the decision is made to proceed, the Safety Review or DLRM voting members will select the appropriate PACAP-38 dose. The decision to proceed with Part B of the study will be based on the goal of ensuring subject safety and ideally triggering headache in all subjects within a given cohort and moderate to severe MLAs in the majority of subjects within a given cohort and mild, moderate or severe MLAs in the majority of subjects within the same cohort may be considered acceptable to advance to Part B of the study.

Part B: Randomization (AMG 334 or Placebo) Phase: A minimum of 16 and a maximum of 36 subjects will be randomized between two treatment groups (AMG 334 or placebo). On Day 1, treatment groups will receive 140 mg IV AMG 334 over 30 minutes or matching placebo, in a one to one allocation ratio. On Day 8, the subjects will be administered the dose of PACAP-38 determined during PACAP-38 Dose Selection. All subjects will remain in-house for 24 hours of observation following PACAP-38 infusion.

Subjects will be monitored and asked questions from the headache questionnaire (Appendix D), as per the Schedule of Assessment in Table 2, to determine if they have experienced a MLA. Previous challenge studies have shown that for migraineurs the median onset of a MLA is within 4 hours with some patients experiencing a MLA as late as 12 hours following PACAP-38 infusion. Therefore a headache questionnaire covering the 24 hours after infusion will ensure capture of all the PACAP-38 induced MLAs. After 24 hours of data from the first 16 Randomized (AMG 334 or Placebo) Subjects challenged with PACAP-38 is available, an interim analysis will be conducted to determine if challenge rates are comparable to historical rates (~66%) and if AMG 334 has greater efficacy than placebo. If AMG 334 is found to completely block PACAP-38 induced migraines, or have the same efficacy as placebo, the study will be terminated. Otherwise, approximately 20 Randomized (AMG 334 or Placebo) Subjects will be added.

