3.3 Number of Subjects

Participants in this clinical investigation shall be referred to as "subjects".

A total of up to 61 migraine subjects are planned to be enrolled into the study. Up to 25 subjects may participate in Part A and up to 36 in Part B of the study. If ambiguous results in Part A occur regarding the ability of PACAP-38 ideally safely trigger a headache in all subjects within a given cohort (although, safely triggering headaches in the majority of subjects within a given cohort may be considered acceptable to advance to Part B of the study) and moderate to severe MLAs in the majority of subjects within the same cohort, then a previously dosed cohort sample size may be expanded to up to 5 subjects per cohort. Once the PACAP-38 dose has been selected, 8 subjects will be randomized to placebo and 8 subjects will be randomized to AMG 334. The data collected for the 16 Randomized (AMG 334 or Placebo) Subjects will be included in the interim analysis (See Section 10.4.1). Following the interim analysis, if the decision is to continue enrollment for the study, an additional 10 subjects will be randomized to AMG 334.

The sample size justification is described in Section 10.2.

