6.3.1.2 Dose-cohort Study Escalation and Stopping Rules for PACAP-38

In order to ensure subject safety and select the lowest PACAP-38 dose that will ideally trigger headache in all subjects within a given cohort and moderate to severe MLAs in

the majority of the subjects within the same cohort, a dose selection strategy, along with Safety Review Meetings and Dose-Level Review Meetings (DLRM) have been implemented. Dosing of PACAP-38 shall not exceed a total dose of 115 pmol/kg, providing an approximate 10X exposure margin over the non-clinical NOAEL dose. However, the trigger of headaches in the majority of the subjects within a given cohort and mild, moderate or severe MLAs in the majority of the subjects within the same cohort may be considered acceptable to advance to the randomized portion of the study (Part B).

Up to five cohorts consisting of approximately 2 to 5 subjects are planned. Based on emerging safety and tolerability data, as well as the number of subjects experiencing a headache and/or MLA, the voting members of the Safety Review Meetings or DLRM (the PI, Medical Monitor and Global Safety Officer), may decide cohorts should be removed or additional cohorts should be added, with a maximum of 5 total cohorts. Subject numbers within each cohort may also be increased or decreased based on the decision from the Safety Review Meeting or DLRM. Doses to be administered within each cohort may be repeated, higher or lower than the last dosed cohort. Dosing of any subject shall not exceed 115 pmol/kg. Possible future PACAP-38 doses and associated cohorts beyond 100 pmol/kg (Cohort 4) are as follows: 115 pmol/kg (Cohort 5).

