If the PI, MM, and GSO or designee decide not to proceed with enrollment into a subsequent cohort, then a Safety Review Meeting or DLRM will be held after the last dosed cohort. Refer to Section 10.4.2 for additional information on the Safety Review Meetings and DLRMs. The Safety Review Meeting or DLRM voting members will decide whether or not to proceed with enrollment in Part B Randomization (AMG 334 or Placebo) Phase and if the decision is made to proceed, the Safety Review or DLRM voting members will select the appropriate PACAP-38 dose. The decision to proceed with Part B of the study will be based on the goal of ensuring subject safety and ideally triggering headache in all subjects within a given cohort and moderate to severe MLAs in the majority of subjects within a given cohort and mild, moderate or severe MLAs in the majority of subjects within the same cohort may be considered acceptable to advance to Part B of the study.

All available study data, including the headache questionnaires, demographics, investigational product administration, medical history, concomitant medications, adverse events (including MLA), ECGs, vital signs, and laboratory results will be reviewed. Data to be reviewed at the DLRMs during the PACAP-38 Dose Selection Phase will not be blinded. Data to be reviewed for any unscheduled DLRM post the PACAP-38 Dose Selection Phase will be reviewed blinded (ie, treatment assignment will not be revealed) unless unblinding is deemed necessary for the review team to make

dosing decisions. If deemed necessary, unblinding will be performed to assist dose decisions in accordance with Amgen standard procedures.

6.3.1.3 PACAP-38 - Dosage Adjustments, Delays, Rules for Withholding, or Restarting Stopping or Permanent Discontinuation

Dosing of PACAP-38 will be stopped or modified by the DLRM voting members if suspected unexpected treatment related adverse events of Grade 2 or greater in the same system organ class occur in 2 or more subjects or Grade 3 occur in 1 or more subject. Dosing of PACAP-38 will also be stopped or modified by the DLRM voting members under the following circumstances:

- a) Blood pressure:
 - a. Systolic BP > 150 mm Hg OR
 - b. Diastolic BP > 100 mm Hg OR
 - c. Decrease in SBP from baseline > 30 mm Hg OR
 - Decrease in DBP from baseline > 15 mm Hg and considered clinically relevant after consultation between the investigator and the medical monitor.

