Any changes in blood pressure as defined above must be confirmed with 3 consecutive measurements taken approximately 5 minutes apart and with the subject remaining in a semi-recumbent position. The mean of the 3 measurements will be the final recorded value.

- b) Mean heart rate increase of subjects in a given cohort is greater than 50% or greater than 20% decrease over baseline during a 2 hour period after dosing
- c) Changes in other vital signs or clinical laboratory results considered to pose a significant health risk to subjects

In addition, any clinically or medically significant suspected adverse drug reactions and serious adverse events considered to be related to study procedures will be followed until resolved or considered stable.

The study may be terminated at any point in time at the discretion of the sponsor.

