95%	72% 73%	36% 40% 50%	6% 8% 15% 40%	20% 35% 50% 70%	AMG 334 subjects with MLA

Probability of Overall Trial Success:

Placebo subjects with MLA

20	%	35%	50%	70%		
1	%	14% 4%	48% 23% 6%	91% 72% 38% 5%	20% 35% 50% 70%	AMG 334 subjects with MLA

From the above, it can be seen that, if PACAP-38 does not induce a sufficient proportion of MLA for the study to test the hypothesis, or AMG 334 appears to be ineffective in blocking PACAP-38 induced MLA, the trial is more likely to fail at the interim analysis stage (highlighted in bold and underlined in the results with respect to the probability of fail at the interim analysis). However, should the study continue from the interim analysis stage, even by chance, the overall type I error is controlled such that the study is highly unlikely to conclude AMG 334 is effective in blocking PACAP-38 induced MLA (overall trial success) when it is not (highlighted in bold and underlined in the results with respect to the probability of overall trial success).

Designated personnel from Biostatistics will be unblinded for the interim analysis (see Section 10.3). After interim analysis, the designated unblinded Biostatistics personnel will recommend to the study team whether the sample size remains at 8 per group or needs to be increased to 18 per group.

10.4.2 Data Monitoring Committee (DMC), Data Review Team (DRT) or Dose Level Review Team (DLRT)

A Safety Review Meeting or DLRM will be held after PACAP-38 dosing has been completed in each cohort in Part A. Available vital signs and adverse events occurring at least 24 hours following PACAP-38 dosing for each cohort will be reviewed by the PI,

MM, and GSO or designee to decide enrollment in subsequent cohort. If the PI, MM, and GSO or designee decide not to proceed with enrollment in the subsequent cohort, then a Safety Review Meeting or DLRM will be held after the last dosed cohort.

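### In the supplied Amendment 3, the only numeric heart-rate stopping limit for PACAP-38 is a cohort mean, so its unit and timing are undefined in Part B

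*Protocol*

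**What the plan says.** Protocol section 6.3.1.3 gives the voting members of the Dose Level Review Meeting (DLRM) four grounds for stopping or modifying PACAP-38. Nothing in it restricts them to Part A.

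- **Adverse events:** "suspected unexpected treatment related adverse events of Grade 2 or greater in the same system organ class" in two or more subjects, or a Grade 3 event in one.
- **Item a, blood pressure:** systolic above 150 or diastolic above 100 mm Hg, or a fall from baseline of more than 30 systolic or 15 diastolic (the diastolic fall also to be judged clinically relevant). "Any changes in blood pressure as defined above must be confirmed with 3 consecutive measurements taken approximately 5 minutes apart", so the limit is applied to the individual.
- **Item b, heart rate:** "Mean heart rate increase of subjects in a given cohort is greater than 50% or greater than 20% decrease over baseline", over the 2 hours after dosing.
- **Item c:** "Changes in other vital signs or clinical laboratory results considered to pose a significant health risk to subjects".

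On the meaning of a cohort, section 6.3.1.2 says "Up to five cohorts consisting of approximately 2 to 5 subjects are planned", within dose selection, and section 10.4.2 says "A Safety Review Meeting or DLRM will be held after PACAP-38 dosing has been completed in each cohort in Part A". Section 3.1 describes Part B as 16 to 36 subjects randomized to two treatment groups, each subject receiving PACAP-38 on Day 8.

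Section 6.3.1.2 uses the same 50% figure again. There, a mean rise above 50% in Cohort 1, with blood pressure within limits, is the condition for dosing Cohort 2, and the criteria are reused for later cohorts.

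SAP section 1 is written to Protocol Amendment 4 (21 Oct 2016), which was not supplied.

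**The concern.** The sponsor thought a numeric heart-rate limit for the challenge agent worth writing down. As worded, it is tied to a grouping that Amendment 3 uses only in dose selection. In Part B the protocol does not say whether the mean is taken over an arm, over all subjects so far, or over some other set, nor when it is taken. Whether a marked heart-rate change in one Part B subject holds up the next infusion therefore rests on judgement, while the same subject's blood pressure is held to written limits.

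The 50% figure also points in opposite directions in two adjoining sections, so it cannot be carried into Part B until its direction is settled.

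**Working it through.** **1. Which limits can be applied in which part (section 6.3.1.3)**

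| Ground | Unit | Heart-rate number? | Usable in Part B as written? |
|---|---|---|---|
| Adverse-event limb | count of subjects | no | yes |
| Item a, blood pressure | individual subject | no | yes |
| Item b, heart rate | mean of a cohort | yes | unit and timing undefined |
| Item c | judgement | no | yes, though its reference to other vital signs follows the heart-rate item and could be read as excluding heart rate |

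The remaining heart-rate numbers in the protocol are the cohort-mean escalation condition in 6.3.1.2 and the baseline exclusion above 85 beats/min (4.2.11). Neither is a Part B stopping limit. The SAP repeats the cohort-mean condition for Part A and adds no other heart-rate limit.

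**2. What a pooled Part B mean would detect**

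Let n subjects be averaged, one with rise x and the others with rise r. The mean is [x + (n − 1)r]/n, so a mean of 50% needs x = 50n − (n − 1)r. The documents give no individual heart-rate rises, so r = 20% to 30% is an assumption.

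| n | x needed at r = 20% | x needed at r = 30% | mean if x = 100% |
|---|---|---|---|
| 2 (small cohort) | 100 − 20 = 80% | 100 − 30 = 70% | 60% to 65% |
| 5 (largest cohort) | 250 − 80 = 170% | 250 − 120 = 130% | 36% to 44% |
| 8 (one arm at interim) | 400 − 140 = 260% | 400 − 210 = 190% | 30% to 39% |
| 16 (all at interim) | 800 − 300 = 500% | 800 − 450 = 350% | 25% to 34% |

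In a cohort of two, one subject whose heart rate doubles takes the mean over 50%. Among 16 the same subject leaves it far below.

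**3. Why a per-subject version needs an absolute limit for rises**

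From an assumed baseline of 60, a 50% rise is 1.5 × 60 = 90 beats/min. From the highest eligible baseline, 85, it is 1.5 × 85 = 127.5. Now require the rise to exceed 50% and the rate to exceed L, with illustrative L = 100, 110 or 120.

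- L governs for baselines below L/1.5 = 67, 73 or 80.
- From 60 the rise needed is 100/60, 110/60 or 120/60, that is +67%, +83% or +100%.
- From 85 the 50% limb governs throughout, because 127.5 exceeds 120.

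For falls, 0.8 × 85 = 68 and 0.8 × 60 = 48 beats/min, so a floor may be wanted as well.

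**4. Direction of the 50% figure**

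Section 6.3.1.2 says that a mean rise above 50% with acceptable blood pressure allows Cohort 2 to start. Section 6.3.1.3 item b says that the same rise stops or modifies dosing. Both cannot be intended.

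**The case against.** **A cohort mean suits dose selection.** It asks whether a dose level is tolerable, and the Part B dose is chosen only after that review. An infusion lasts at most 11.5 minutes, the half-life is given as 3.5 minutes and the first scheduled reading after dosing is at 0.25 hours. A per-subject limit would therefore mainly protect later subjects. This stands, and it is why the fix governs the next infusion.

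**A mean can be computed in Part B.** All Part B subjects receive one selected dose, so a pooled mean needs no unblinding. A reader might infer from item b that no heart-rate limit could be evaluated in Part B at all. The documents do not support that. The limit is undefined there and insensitive to one subject, but it is not impossible to compute.

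**Other safeguards remain.** A reader might also infer that heart rate goes unwatched in Part B. It does not.

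- A study physician is present at dosing (6.3.1).
- Vital signs and ECGs are scheduled repeatedly on Day 8 (Table 2) and named as risk mitigation (2.3, 2.4).
- Any voting member, including the investigator, can call an unscheduled DLRM, which reviews vital signs, and the PACAP-38 dose can be changed later (10.4.2).

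This stands as to oversight, but none of these carries a heart-rate number. A transient rise is listed as expected (2.4), so it would not by itself meet the unexpected-event limb, although a marked or sustained one might. The continuing review in 9.2.2.4 names adverse events and safety laboratory results, not vital signs.

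**No stopping criterion was met.** The Amendment 3 summary says so with four cohorts dosed, up to 100 pmol/kg. This is the only evidence available and it points to low practical impact. Its weight is limited: the cohorts held 2 + 3 + 2 + 4 = 11 subjects, the review meeting for the 100 pmol/kg cohort was still to come, and the heart-rate criterion was itself a cohort mean. It does not show how far any individual's rate rose.

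**Conclusion.** The point holds for the supplied Amendment 3 text as a minor gap that is cheap to close. The only numeric heart-rate limit for PACAP-38 has no defined unit or timing in Part B, and the natural substitute, a pooled mean, would barely register one subject's reaction. The separate contradiction over the direction of the 50% figure is plain on the page.

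Under Amendment 3 the gap concerns the 16 to 36 randomized subjects who receive PACAP-38. A reader might express this as a share of all subjects: with 25 in Part A, 16/41 = 39% to 36/61 = 59%. That holds only for the Amendment 3 layout. In SAP section 3.1, Part A responders re-enter Part B and PACAP-38-naïve subjects are challenged before randomization, so the two parts no longer add up to distinct people and non-responders are exposed without being randomized.

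These counts describe exposure to an undefined rule, not expected harm. The documents contain no individual heart-rate data from which to estimate how often a limit would be met. The dilution figures rest on the assumed 20% to 30% rise in the other subjects. Amendment 4 may already have changed item b.

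**What to change.** Check Amendment 4 first. If item b is unchanged there:

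1. **Apply item b per subject in Part B.** The trigger is a rise above 50% or a fall above 20% within 2 hours of PACAP-38, confirmed on repeat. Name the baseline as the value before PACAP-38 on that day, because the SAP default is the last value before investigational product. Protocol 10.5.3.2 already uses Day 8 pre-dose for ECGs after PACAP-38.
2. **For rises, also require an absolute heart rate,** set by the sponsor and investigator from individual Part A readings. The 100 to 120 beats/min values above are illustrations only. Consider a floor for falls in the same way.
3. **State the consequence in 6.3.1.3 and 10.4.2:** meeting the limit prompts a blinded review by the existing voting members before the next PACAP-38 infusion. No new committee is needed.
4. **Correct 6.3.1.2** so that escalation requires the mean heart-rate rise not to exceed 50%, in line with item b.

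The cost is protocol wording. Table 2 already schedules heart rate before PACAP-38 and at 0.25, 0.5, 1 and 2 hours; only the confirmatory repeat is added. The downside is an occasional ad hoc review and a short pause in Part B challenges. The absolute limit keeps these down, since some rise is expected.

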6.4 Criteria for Additional Safety Assessment Due to Potential Hepatotoxicity

Following the single-dose administration of study drug, the subject should be followed according to the recommendations in Appendix A (Additional Safety Assessment

Information) for possible drug-induced liver injury (DILI), if ALL of the criteria below are met:

- TBL > 2x upper limit of normal (ULN) or INR > 1.5
- AND increased AST or ALT from the relevant baseline value as specified below:

Baseline AST or ALT Value	AST or ALT Elevation
< ULN	≥ 3x ULN

- AND no other cause for the combination of the above laboratory abnormalities is immediately apparent; important alternative causes for elevated AST/ALT and/or elevated TBL values include, but are not limited to:
 - o Hepatobiliary tract disease
 - Viral hepatitis (eg, hepatitis A/B/C/D/E, Epstein-Barr virus, cytomegalovirus, herpes simplex virus, varicella, toxoplasmosis, and parvovirus)
 - Right sided heart failure, hypotension, or any cause of hypoxia to the liver causing ischemia
 - Exposure to hepatotoxic agents/drugs or hepatotoxins including herbal and dietary supplements, plants, and mushrooms
 - Heritable disorders causing impaired glucuronidation (eg, Gilbert's syndrome, Crigler-Najjar syndrome) and drugs that inhibit bilirubin glucuronidation (eg, indinavir, atazanavir)
 - Alpha-one antitrypsin deficiency
 - Alcoholic hepatitis
 - Autoimmune hepatitis
 - Wilson's disease and hemochromatosis
 - o Nonalcoholic fatty liver disease including steatohepatitis
 - Non-hepatic causes (eg, rhabdomyolysis, hemolysis)

6.5 Concomitant Therapy

Throughout the study, investigators may prescribe any concomitant medications or treatments deemed necessary to provide adequate supportive care except for those listed in Section 6.9. Concomitant therapies are to be collected from informed consent through the EOS. Details (name, indication and dates) of all concomitant medications will be recorded in the subject's source documents and on the eCRF.

6.6 Alcohol and Tobacco Restrictions

A urine screen for drugs of abuse (cannabis, cocaine, amphetamines, benzodiazepines, opiates, barbiturates) and urine (or breath) ethanol screens will be performed at the time points referenced in the schedule of assessments.

Subjects are not permitted to consume any alcohol within 24 hours of study enrollment. During the study, the use of alcohol by adults will be limited to no more than 1 drink per day (one drink being equivalent to 12 ounces of regular beer, 5 ounces of wine, or 1.5 ounces of 80 proof distilled spirits). Subjects must refrain from alcohol consumption for the 24-hour period prior to study visits.

The use of nicotine or tobacco containing products (including but not limited to: snuff, chewing tobacco, cigars, cigarettes, pipes, or nicotine patches) will not be permitted throughout the study. A recent nicotine or tobacco user (should have stopped approximately 6 months prior to screening) must be excluded.

6.7 Other Treatment Procedures

6.7.1 Caffeine Restrictions

Throughout the study (beginning at screening), subjects will continue their usual caffeine intake, but not to exceed 2 cups per day (or the equivalent total daily intake of less than 200 mg caffeine per day).

6.7.2 Exercise Restrictions

Subjects are required to refrain from strenuous exercise beginning at screening until the end of study.

6.7.3 Oral Hydration

Subjects are required to receive oral hydration (~500 mL of water) within 1 hour prior to the start of PACAP-38 infusion.

6.8 Product Complaints

A product complaint is any written, electronic or oral communication that alleges deficiencies related to the identity, quality, durability, reliability, safety, effectiveness, or performance of a drug after it is released for distribution to market or clinic by either Amgen or by distributors and partners for whom Amgen manufactures the material. This includes any drug provisioned and/or repackaged /modified by Amgen. Drug includes investigational product.

Any product complaint associated with an investigational product (AMG 334) or non-investigational product (PACAP-38) supplied by Amgen or designee are to be reported according to the instructions provided in the IPIM.

